11.0 Risks

Subjects may experience nausea and diarrhea, which is a side effect of misoprostol; subjects may have a higher incidence of meconium stained fluid while using misoprostol; uterine tachysystole with or without nonreassuring fetal heart tones; development of chorioamnionitis; need for cesarean section; neonatal morbidity or death. All of these risks are standard risks of labor and delivery should not be any higher incidence due to the study. There is always a discomfort with sterile vaginal exams. As part of the randomization, if the subject is selected to be in the misoprostol administered per vagina, the placement of the medication may cause more discomfort than the subjects that take the medication by mouth.

Side Effects/Risks of Misoprostol:

- Diarrhea: when taking misoprostol 800 mcg daily, trials have shown an incidence of diarrhea of about 13%. In this study you will be not receive more than 300 mcg of misoprostol. [1]
- Use of vaginal misoprostol has a higher rate of uterine contractions, with contractions being more frequent than every 2 minutes when compared with placebo (RR 3.52), dinoprostone gel (RR 1.99), or oxytocin (RR 2.24) for induction of labor. [6] Induction with Foley catheter has a decreased risk of uterine contractions happening greater than every 2 minutes when compared to vaginal misoprostol (RR 0.15). [7]
- Increased risk of meconium staining of amniotic fluid, but no difference in neonatal outcome. [3,6]
- Uterine rupture [1]

Side effects of misoprostol when taken as prescribed for prevention of gastric ulcers that have an incidence greater than 1%, but no difference than placebo. [1]

- Nausea – 3.2%
- Flatulence – 2.9%
- Headache – 2.4%
- Dyspepsia – 2%
- Vomiting – 1.3%
- Constipation – 1.1%

There is a risk, as with any medication, of an unexpected allergic reaction to the study drug (defined as the development of hives, rash, swelling, or difficulty breathing) which will be treated with antihistamines in a standard fashion and lead to immediate withdrawal of the subject from the trial.

There is a risk of loss of confidentiality if protected health information or identity is obtained by someone other than the investigators, but precautions will be taken to prevent this from happening.

12.0 Potential Benefits to Subjects and Others

12.1 Potential Benefits to Subjects

Subjects may benefit from a faster labor induction, less need for vaginal exams, easier to administer misoprostol for induction of labor, less risk of infection, and decreased rate of cesarean section.

12.2 Potential Benefits to Others

This research may show that misoprostol has a similar or better effect when given orally as compared to vaginal administration. Given orally may result in better patient satisfaction, less demand on licensed practitioner during induction of labor, less rate of infection, and less cesarean section rate.

13.0 Sharing Results with Subjects

There are no results from diagnostic studies that will be obtained. The study results will be shared with the subjects at the end of the project.

14.0 Subject Stipend (Compensation) and/or Travel Reimbursements

There is no compensation or reimbursement that will be given to these subjects.

15.0 Economic Burden to Subjects

15.1 Costs

The misoprostol medication will be provided to the subjects at no cost. There are no extra costs that subjects are responsible for because of their participation in this research study. Subjects will assume the normal charges from the hospital and staff for Labor and Delivery and Postpartum care.

15.2 Compensation for research-related injury

It is the policy of the institution to provide neither financial compensation nor free medical treatment for research-related injury. In the event of injury resulting from this research, medical treatment is available but will be provided at the usual charge. Costs for the treatment of research-related injuries will be charged to subjects or their insurance carriers.

16.0 Resources Available

16.1 Facilities and locations

Identification and notification of subjects will take place at all office locations within the Penn State Women's Health Division, including Hope Drive, Nyes Road, Camp Hill, and Mt. Joy office. Recruitment, consent, and study procedures will be performed at Penn State Hershey Medical Center, Labor and Delivery Unit.

16.2 Feasibility of recruiting the required number of subjects

From previous data at Penn State Hershey Medical Center it is estimated that there was about 350 inductions of labor over one year's time. Accounting for inclusion/exclusion criteria it is estimated only 60% of patients will qualify for the study. That leaves 210 patients eligible for the study. Of the 210 potential subjects, 52% would need to be recruited to complete the study for the projected sample size of 110 subjects.

16.3 PI Time devoted to conducting the research

The Co-Investigator will engage in the study over training remaining at Penn State Hershey Medical Center. During her training, there is devoted research time in her residency program for a research project such as this one. Assistance from other project members will be provided including [name], PI of this project who has dedicated research time. [name] when not in clinic, will have devoted time dedicated to research projects. As PI, she will ensure that an allotted time will be well suited to oversee the project with the Co-PI.

16.4 Availability of medical or psychological resources

Routine intrapartum and postpartum care. There is no foreseeable extra medical or psychological resources needed.

16.5 Process for informing Study Team

All study members will have access to the IRB approved protocol and supporting documents. A copy of the study protocol will be available on the Labor and Delivery Unit and in secure location on hersheyfiles.net. We will have training sessions for all parties involved, study members, physicians and nurses, to review the study protocol. We will have ongoing meetings with research team members

for discussions on progress of study and to clarify their duties and expectations to ensure timely completion of study.

17.0 Other Approvals

17.1 Other Approvals from External Entities

N/A

17.2 Internal PSU Committee Approvals

Check all that apply:

Anatomic Pathology – Hershey only – Research involves the collection of tissues or use of pathologic specimens. Upload a copy of the Use of Human Tissue For Research Form on the “Supporting Documents” page in CATS IRB. This form is available on the IRB website at: <http://www.pennstatehershey.org/web/irb/home/resources/forms>

Animal Care and Use – All campuses – Human research involves animals and humans or the use of human tissues in animals

Biosafety – All campuses – Research involves biohazardous materials (human biological specimens in a PSU research lab, biological toxins, carcinogens, infectious agents, recombinant viruses or DNA or gene therapy).

Clinical Research Center (CRC) Advisory Committee – Research involves the use of CRC services in any way.

Conflict of Interest Review – All campuses – Research has one or more of study team members indicated as having a financial interest.

Radiation Safety – Hershey only – Research involves research-related radiation procedures. All research involving radiation procedures (standard of care and/or research-related) must upload the Radiation Review Form on the “Supporting Documents” page in CATS IRB. This form is available on the IRB website at: <http://www.pennstatehershey.org/web/irb/home/resources/forms>

IND/IDE Audit – All campuses – Research in which the PSU researcher holds the IND or IDE or intends to hold the IND or IDE.

Scientific Review – Hershey only – All investigator-written research studies requiring review by the convened IRB must provide documentation of scientific review with the IRB submission. The scientific review requirement may be fulfilled by one of the following: (1) external peer-review process; (2) department/institute scientific review committee; or (3) scientific review by the Clinical Research Center Advisory committee. NOTE: Review by the Penn State Hershey Cancer Institute Scientific Review Committee is required if the study involves cancer prevention studies or cancer patients, records and/or tissues. For more information about this requirement see the IRB website at: <http://www.pennstatehershey.org/web/irb/home/resources/investigator>

18.0 Multi-Site Research

N/A

19.0 Adverse Event Reporting

19.1 Adverse Event Definitions

For drug studies, incorporate the following definitions into the below responses, as written:	
Adverse event	Any untoward medical occurrence associated with the use of the drug in humans, whether or not considered drug related
Adverse reaction	Any adverse event caused by a drug
Suspected adverse reaction	Any adverse event for which there is a reasonable possibility that the drug caused the adverse event. Suspected adverse reaction implies a lesser degree of certainty about causality than “adverse reaction”. 
 • Reasonable possibility. For the purpose of IND safety reporting, “reasonable possibility” means there is evidence to suggest a causal relationship between the drug and the adverse event.
Serious adverse event or Serious suspected adverse reaction	Serious adverse event or Serious suspected adverse reaction: An adverse event or suspected adverse reaction that in the view of either the investigator or sponsor, it results in any of the following outcomes: Death, a life-threatening adverse event, inpatient hospitalization or prolongation of existing hospitalization, a persistent or significant incapacity or substantial disruption of the ability to conduct normal life functions, or a congenital anomaly/birth defect. Important medical events that may not result in death, be life-threatening, or require hospitalization may be considered serious when, based upon appropriate medical judgment, they may jeopardize the patient or subject and may require medical or surgical intervention to prevent one of the outcomes listed in this definition.
Life-threatening adverse event or life-threatening suspected adverse reaction	An adverse event or suspected adverse reaction is considered “life-threatening” if, in the view of either the Investigator (i.e., the study site principal investigator) or Sponsor, its occurrence places the patient or research subject at immediate risk of death. It does not include an adverse event or suspected adverse reaction that had it occurred in a more severe form, might have caused death.
Unexpected adverse event or Unexpected suspected adverse reaction.	An adverse event or suspected adverse reaction is considered “unexpected” if it is not listed in the investigator brochure, general investigational plan, clinical protocol, or elsewhere in the current IND application; or is not listed at the specificity or severity that has been previously observed and/or specified.

19.2 Recording of Adverse Events

In accordance with applicable policies of The Pennsylvania State University Institutional Review Board (IRB), the investigator will report, to the IRB, any observed or reported harm (adverse event) experienced by a subject or other individual, which in the opinion of the investigator is determined to be (1) unexpected; and (2) probably related to the research procedures. Harms (adverse events) will be submitted to the IRB in accordance with the IRB policies and procedures.

19.3 Causality and Severity Assessments

The investigator will promptly review documented adverse events and abnormal test findings to determine 1) if the abnormal test finding should be classified as an adverse event; 2) if there is a reasonable possibility that the adverse event was caused by the study drug(s) or device(s); and 3) if the adverse event meets the criteria for a serious adverse event.

If the investigator's final determination of causality is "unknown and of questionable relationship to the study drug(s) or device(s)", the adverse event will be classified as associated with the use of the study drug(s) or device(s) for reporting purposes. If the investigator's final determination of causality is "unknown but not related to the study drug(s) or device(s)", this determination and the rationale for the determination will be documented in the respective subject's case history.

19.4 Reporting Adverse Reactions and Unanticipated Problems to the Responsible IRB

In accordance with applicable policies of The Pennsylvania State University Institutional Review Board (IRB), the investigator will report, to the IRB, any observed or reported harm (adverse event) experienced by a subject or other individual, which in the opinion of the investigator is determined to be (1) unexpected; and (2) probably related to the research procedures. Harms (adverse events) will be submitted to the IRB in accordance with the IRB policies and procedures.

19.5 Unblinding Procedures

The study is not blinded, therefore N/A

19.6 Stopping Rules

If the total number of subjects experiencing one or more serious adverse events (defined as uterine rupture, maternal death during her hospitalization, neonatal death during maternal hospitalization, and cesarean hysterectomy) reaches 5, the trial will be stopped. This reflects a 2.3% prevalence rate (110 subjects with 110 singleton neonates are included in the trial for a prevalence of 5/220 subjects). Or if any two cases of uterine rupture, two cases of maternal death during her hospitalization, or two cases of neonatal death (0-28 days of life) related to the study drug, the trial will be stopped.

20.0 Study Monitoring, Auditing and Inspecting

20.1 Study Monitoring Plan

20.1.1 Quality Assurance and Quality Control

The study will be monitored by Clinical Trial Monitoring Team from the Department of Public Health Sciences at Penn State Hershey College of Medicine. The monitors will provide an independent review of the regulatory and subject records and data collected to assure compliance with the protocol, GCP, and applicable federal regulations. The monitoring will occur at regular intervals after the enrollment of the first subject, after enrollment of the fifth subject and then after every 10 subjects enrolled or at a frequency developed by the Public Health Sciences monitoring team.

20.1.2 Safety Monitoring

On the listed protocol that investigators will follow while carrying out the study, will be the list of treatment emergent serious adverse events (TESAEs). Treatment emergent serious adverse events are defined as maternal death during hospital admission, neonatal death (0-28 days of life) related to the study drug, uterine rupture, or cesarean hysterectomy. If a TESAE happens the Co-investigator will be immediately paged and notified. If no response within 4 hours, the Principal Investigator, [name], will be paged.

The Principal Investigator will confirm that the TESAE are correctly entered into the adverse event (AE) case report forms by the Co-investigator; be available to answer any questions that the Co-investigator may have concerning AEs; and will notify the IRB and FDA all TESAEs. All assessments of AEs will be made by a licensed medical professional who is an investigator on the research.

The Co-investigator will complete the appropriate report form and logs; assist the PI to prepare reports and notify the IRB and FDA of all Unanticipated Problems/TESAE's.

The Clinical Trial Monitoring Team will confirm that the TESAEs and AEs are correctly entered into the case report forms. The monitoring team will also confirm that the adverse events are consistent with the source documents and are reported to the appropriate regulatory bodies as required.

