1.3 Secondary Study Endpoints

1. Time interval from administration of misoprostol to initiation of oxytocin for continued augmentation of labor
2. Time interval from administration of misoprostol to vaginal delivery
3. Cesarean section rate
4. Rate of vaginal delivery within 24 hours
5. Rate of abandoning misoprostol for cervical ripening and switching to mechanical dilation for cervical ripening (ie, Foley balloon)
6. Rate of development of preeclampsia requiring magnesium sulfate administration
7. Rate of tachysystole
8. Rate of tachysystole causing non-reassuring fetal heart tones
9. Rate of need for tocolysis
10. Rate of chorioamnionitis
11. Rate of meconium stained fluid
12. Neonatal morbidity (composite outcome)
 - a. Apgar of less than 7 at 5 minutes
 - b. Fetal arterial umbilical cord gas with pH of less than 7 or base deficit great than 12
 - c. NICU admission within 4 hours of delivery
13. Maternal side effects
 - a. Rate of anti-emetic use
 - b. Rate of diarrhea
14. Treatment emergent serious adverse events
 - a. Uterine rupture
 - b. Cesarean hysterectomy
 - c. Maternal death during her hospitalization
 - d. Neonatal death (0-28 days of life) related to the study drug
15. Adverse events
 - a. Postpartum hemorrhage requiring blood transfusion
 - b. Maternal surgical ICU admission
 - c. Neonatal NICU admission during mother's hospital admission

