10.3 Method of collection of safety information

All TESAEs (uterine rupture, maternal death during her hospitalization, neonatal death (0-28 days of life) related to the study drug, and cesarean hysterectomy) will be documented on study specific case report forms. Co-PI, with [name] as second contact, will be notified immediately to begin process of notifying the IRB within 24 hours if the event is a TESAE.

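### Neonatal death is an endpoint only when judged drug-related, so the one between-arm comparison of deaths rests on unblinded attribution

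*Combined protocol and SAP*

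**What the plan says.** Section 20.1.2 lists the four TESAEs: maternal death during the admission, "neonatal death (0-28 days of life) related to the study drug, uterine rupture, or cesarean hysterectomy". It continues: "If a TESAE happens the Co-investigator will be immediately paged and notified". It also states: "All assessments of AEs will be made by a licensed medical professional who is an investigator on the research".

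Endpoint 14d in Section 1.3 is worded the same way: "Neonatal death (0-28 days of life) related to the study drug". Section 10.2 repeats the restricted definition and attaches the 24-hour IRB report to it. Section 10.3 repeats it again and says that these events "will be documented on study specific case report forms". Section 10.8 uses it in the five-subject stopping count.

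On causality, Section 19.3 begins: "The investigator will promptly review documented adverse events and abnormal test findings to determine". Relatedness is one of the things then determined. Section 19.2 is headed as the recording section, but its text is the IRB-reporting rule of 19.4. It covers harms "which in the opinion of the investigator is determined to be (1) unexpected; and (2) probably related to the research procedures".

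Two places define the event differently. Section 3.3.1 lists neonatal death during hospitalization among the serious adverse events, with no causality condition. The five-subject count in Section 19.6 uses neonatal death during the mother's hospitalization, also with no causality condition.

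**The concern.** Whether a neonate died is a fact. Whether the death was caused by the drug is a judgement, and Section 7.4.5 says there is no blinding, so whoever makes that judgement knows the route. Building the judgement into the event definition has two consequences.

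- **Capture.** The TESAE page, form and IRB notice start only once a death carries the label. Section 19.3 places the causality judgement after documentation, but for this one event the definition presupposes it. A death regarded as unrelated has no explicitly stated path to the people who are meant to assess it.
- **Comparison.** Section 8.3 compares endpoints 3-15 between arms. For neonatal death, what is compared is the number of deaths attributed to misoprostol. A reader of the results could not recover the number of deaths from any listed endpoint.

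**Working it through.** **1. Compare the definitions.**

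- Drug-related death at 0-28 days only: endpoint 14d, Sections 10.2, 10.3, 10.8 (both stopping limbs) and 20.1.2, and the two-case limb of 19.6.
- In-hospital neonatal death, no causality condition: Section 3.3.1 and the five-subject limb of 19.6.

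Sections 10.8 and 19.6 therefore state the same five-subject rule with different events. Both quote 5/220 = 2.27%, which reproduces their 2.3%. That figure does not depend on which deaths count, so it cannot settle which definition was intended.

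**2. Look for an endpoint that counts all neonatal deaths.** Item 12 is Apgar score, cord gas and early NICU admission. Item 14d requires relatedness. Item 15 is transfusion, maternal ICU admission and NICU admission. None counts neonatal death from any cause. The other adverse events named for review in Section 10.2 match item 15 and do not include it.

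**3. Look for another reporting route.** Sections 19.2 and 19.4 require an event to be both unexpected and probably related. Section 11 lists neonatal death as a risk. Under 19.1, an event listed in the protocol is not unexpected unless its specificity or severity is new. An unrelated neonatal death fails the second condition and would ordinarily fail the first.

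**4. Size.** The documents give no neonatal death rate. Assume a risk p of 0.1%, 0.2% or 0.5% from any cause, with n = 110 neonates (Section 8.1; singletons).

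- Expected deaths, 110p: 0.11, 0.22, 0.55.
- Chance of at least one death, 1 − (1 − p)^110: 10.4%, 19.8%, 42.4%.
- Chance of two or more: 0.6%, 2.1%, 10.5%.

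Now let a share s of deaths be judged related. The chance that 14d records at least one is 1 − (1 − ps)^110. At s = 0.5 (assumed) this is 5.4%, 10.4% and 24.1%. At s = 0 it is zero whatever p is.

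**5. Effect on the test.** With 55 per arm, one death gives a two-sided Fisher p of 1. Two deaths in the same arm give 2 × C(55,2)/C(110,2) = 2 × 1485/5995 = 0.50. Attribution of one or two deaths cannot make the 14d comparison significant or stop it being so. It can decide whether the published count is zero, one or two.

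**The case against.** A reader might infer that an unrelated death would go undocumented, or that the assessing investigators learn of a death only after someone else has labelled it. The documents do not support either reading.

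- The TESAE list is placed "On the listed protocol that investigators will follow while carrying out the study", any licensed professional who is an investigator may assess events, and Section 4.2 has study physicians recruiting, including on Labor and Delivery. An investigator may well know of a death before any page is sent.
- Section 19.1 defines an adverse event without regard to causality, and 19.3 reviews events already documented. Section 20.1.2 has monitors confirm that both TESAEs and other adverse events are correctly entered on the case report forms and agree with source documents.
- Section 19.3 classifies an event of unknown and questionable relationship as associated with the drug for reporting. That works against discarding doubtful cases.
- The five-subject count in 19.6 presupposes that in-hospital deaths are known whatever their cause.

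These points stand, and they limit the concern. General adverse-event recording may capture some or all unrelated deaths. But no section requires it explicitly for neonatal death, the 19.3 safeguard acts only on events already documented, and a death recorded only as an ordinary adverse event does not enter 14d.

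It is also fair to say that deaths will be rare and that Apgar score, cord gas and NICU admission are compared regardless of cause. That lowers the stakes for inference. It does not supply a count of deaths.

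**Conclusion.** The concern holds in a limited form. The TESAE definition makes neonatal death conditional on drug-relatedness, which the other three TESAEs do not require, and paging, the TESAE form and the 24-hour report follow from it. No explicit step routes every neonatal death to an investigator before relatedness is judged. No endpoint counts neonatal death from any cause, so the only neonatal-death endpoint compared between arms depends on unblinded attribution. Separately, Sections 3.3.1 and 19.6 conflict with 10.8 on which neonatal deaths are meant.

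The effect is on the completeness and neutrality of safety reporting. Under the assumed 0.1% to 0.5% risk, the trial has a 10% to 42% chance of seeing any neonatal death. The primary analysis is untouched, and no test result is likely to change. The rates and the share judged related are assumptions. The textual findings do not depend on them. The change should be made because it is cheap and the count matters to readers.

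**What to change.** - **Endpoint 14d, Sections 10.2, 10.3 and 20.1.2:** define the event as neonatal death at 0-28 days from any cause. Notify and document every known death, and tabulate by arm. Add a separate form field for relatedness, completed afterwards under 19.3, and report related deaths as a subset.
- **Section 19.2:** replace the duplicated text with a statement that events are recorded regardless of expectedness or relatedness. Leave that filter to 19.4.
- **Sections 3.3.1, 10.8 and 19.6:** reconcile with each other and with the revised definition. Section 10.8 needs explicit attention because it restates the TESAE definition inside the stopping count. Which neonatal deaths count toward stopping the trial is for the sponsor to decide.

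The cost is protocol wording, one form field and an occasional notification of a death later judged unrelated. No additional patients are needed. One limit should be stated with the results. Section 7.3 ends participation at delivery, Section 10.4 collects data on Labor and Delivery, and no procedure is given for finding deaths after discharge. That gap already applies to the 0-28 day window of 14d and is not created by this change. Deaths after discharge should be reported as far as ascertained.
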